5.5 Treating the patient

5.5.1 Patient numbering

[REDACTED] Once assigned to a patient, the Subject Number will not be reused.

Once

Upon signing the informed consent form, the patient is assigned the next sequential number by the investigator. The investigator or his/her staff will contact the IRT and provide the requested identifying information for the patient to register them into the IRT. The site should select the CRF book with a matching Subject Number from the EDC system to enter data.

The previous Subject-ID of TRAPS patients previously participating in CACZ885D2203 or CACZ885D2207M will be collected in the CRF.

If the patient fails to be treated for any reason, the IRT must be notified within 2 days that the patient was not treated. The reason for not being treated will be entered into the respective electronic CRF page.

5.5.2 Dispensing the investigational treatment

Each study site will be supplied by Novartis with investigational treatment in packaging of identical appearance.

The investigational treatment packaging/ kit has a 2-part label. A unique medication number is printed on each part of this label. The kit(s) dispensed will be the appropriate drug and quantity appropriate to the respective treatment arm and dose level. Investigator staff will identify the investigational treatment package(s) to dispense to the patient by contacting the IRT and obtaining the medication number(s). Immediately before dispensing the package to the patient, investigator staff will detach the outer part of the label from the packaging and affix it to the source document (Drug Label Form) for that patient's unique subject number.

5.5.3 Handling of study treatment

5.5.3.1 Handling of investigational treatment

Investigational treatment must be received by a designated person at the study site, handled and stored safely and properly, and kept in a secured location to which only the investigator and designees have access. Upon receipt, all investigational treatment should be stored according to the instructions specified on the labels. Clinical supplies are to be dispensed only in accordance with the protocol. Technical complaints are to be reported to the respective Novartis CPO Quality Assurance.

Medication labels will be in the local language and comply with the legal requirements of each country. They will include storage conditions for the investigational treatment but no information about the patient except for the medication number.

The investigator must maintain an accurate record of the shipment and dispensing of investigational treatment in a drug accountability log. Monitoring of drug accountability will be performed by monitors during site visits or remotely and at the completion of the trial. Patients will be asked to return all unused investigational treatment and packaging at the end of the study or at the time of discontinuation of investigational treatment.

At the conclusion of the study, and as appropriate during the course of the study, the investigator will return all unused investigational treatment, packaging, drug labels, and a

copy of the completed drug accountability log to the Novartis monitor or to the Novartis address provided in the investigator folder at each site.

5.5.3.2 Handling of other investigational treatment

Not applicable.

5.5.4 Instructions for prescribing and taking investigational treatment

The s.c. injections of investigational treatment may be administered into the patient's arm or thigh. Detailed instructions on the preparation and administration of the study drugs will be described in the Pharmacist Manual and provided to each site.

All patients will receive a first single s.c. injection of investigational treatment at Baseline. Following Baseline, patients will receive injections every 4 weeks until Day 113. Those patients who will be eligible for blinded escape ([Section 3.1.2.2](#)) will receive an additional s.c. injection of investigational drug between Day 8 and Day 28.

Depending on a patient's treatment assignment, i.e. blinded escape, or open-label treatment arm, patients will receive 1 or 2 injections per visit.

Patients, who will be eligible for randomized withdrawal in Epoch 3, will receive injections every 8 weeks till Day 281.

Patients in the open-label treatment arm (Epoch 2, Epoch 3 and or Epoch 4) will receive 1 or 2 injections every 4 or 8 weeks, depending upon individual need until TD/ PSW.

A graphical layout of the patient flow and administration of individual investigational treatment doses is shown in [Figure 3-2](#) and [Figure 3-3](#). Details about the doses administered are also described in [Section 5.2](#).

All dosages prescribed and dispensed to the patient and all dose changes during the study must be recorded on the Dosage Administration Record CRF.

All kits of investigational treatment assigned by the IRT will be recorded/ databased in the IRT.

5.5.5 Permitted dose adjustments and interruptions of study treatment

Any other investigational treatment dose adjustments than detailed in [Section 3.1.2](#) (Epoch 2), [Section 3.1.3](#) (Epoch 3) or [Section 3.1.4](#) (Epoch 4) and/ or interruptions are not permitted.

5.5.6 Rescue medication

Increase of corticosteroid maintenance dose or intermittent steroid treatment up to the dose detailed in [Table 5-1](#) may be used as rescue therapy.

Standard doses of NSAIDs can be used from Day 15 inclusive on an as needed basis to treat the sign and symptoms of TRAPS, HIDS or crFMF during acute flares at the discretion of the investigator. Before Day 15, NSAIDs should not be used for treating any signs or symptoms of the index flare.

Use of rescue medication must be recorded on the concomitant medications page in the CRF.

5.5.7 Concomitant treatment

The investigator should instruct the patient to notify the study site about any new medications he/she takes after the patient was enrolled into the study. All medications, procedures and significant non-drug therapies (including physical therapy and blood transfusions) administered after the patient was enrolled into the study must be recorded.

5.5.8 Prohibited Treatment

Use of the treatments displayed in [Table 5-1](#) is NOT allowed after Screening.

Table 5-1 Prohibited treatment

Medication	Action to be taken
Corticosteroid maintenance (prednisone equivalent > 0.2 mg/ kg/ day or greater than the maximum of 15 mg/ day for children over 60 kg).	Investigational treatment does not need to be discontinued as a result of this protocol deviation (PD)
Anakinra	Investigational treatment to be discontinued ²
Rilonacept, tocilizumab, rituximab and any other biologics ¹ (investigational or marketed)	Investigational treatment to be discontinued ²
Etanercept, adalimumab, infliximab, or any TNF inhibitor (investigational or marketed)	Investigational treatment to be discontinued ²
Leflunomide, thalidomide, cyclosporine, or i.v. Ig	Investigational treatment to be discontinued ²
Tofacitinib	Investigational treatment to be discontinued ²
6-Mercaptopurine, azathioprine, cyclophosphamide, or chlorambucil	Investigational treatment to be discontinued ²
Intra-articular, peri-articular or intramuscular corticosteroid injections	Investigational treatment to be discontinued ²
Any other investigational non-biological drug	Investigational treatment to be discontinued ²
Any live vaccination ¹	Investigational treatment to be discontinued ²
Treatment for tuberculosis	Investigational treatment to be discontinued

¹ It is recommended not to initiate any live vaccination or biologic treatment until 3 months after the last dose of investigational treatment. Killed or inactivated vaccines may be permitted according to the investigator's discretion.

² Investigational treatments must be permanently discontinued but patient will remain in the study and will be followed-up for safety.

5.5.9 Discontinuation of study treatment

Patients may voluntarily discontinue investigational treatment for any reason at any time.

The investigator should discontinue investigational treatment for a given patient if, on balance, he/she believes that continuation would be detrimental to the patient's well-being.

Investigational treatment must be discontinued under the following circumstances:

- Emergence of the following adverse events:
 - a. Absolute QTcF > 500 msec, confirmed by repeat ECG measurements

- b. Serious infections combined with neutropenia CTC grades ≥ 1 ($\text{ANC} < 2.0 \times 10^9/\text{L}$)
- c. CKD as per NKF stages ≥ 4 : $\text{eGFR} \leq 29 \text{ mL/min}/1.73 \text{ m}^2$
- d. Confirmed diagnosis of latent or active TB
- e. Onset of any malignancy
- Any of the following laboratory abnormalities:
 - a. Neutropenia CTC Grades ≥ 2 : $\text{ANC} < 1.5 \times 10^9/\text{L}$
 - b. Thrombocytopenia CTC Grade 4: Platelets $< 10.0 \times 10^9/\text{L}$
- Pregnancy
- Use of prohibited treatment as per [Table 5-1](#)
- Any other protocol deviation that results in a significant risk to the patient's safety

The appropriate personnel from the site and Novartis will assess whether investigational treatment should be discontinued for any patient whose treatment code has been broken inadvertently for any reason.

Patients who discontinue investigational treatment should NOT be considered withdrawn from the study. They should return for the assessments indicated by an asterisk (*) in [Table 6-1](#) or [Table 6-2](#). If they fail to return for these assessments for unknown reasons, every effort (e.g. telephone, e-mail, letter) should be made to contact them as specified in [Section 5.5.11](#).

The investigator must also contact the IRT to register the patient's discontinuation from investigational treatment.

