Patients needing dose escalation in the canakinumab arms, or who escape from placebo arms to canakinumab in the randomized treatment epoch (Epoch 2) or discontinued from the study due to any reason prior evaluating the endpoint at week 16, will be considered as having PGA ≥ 1 and PPGA ≥ 1 . Patient/parent's global assessment of disease activity (PPGA) will also be summarized for weekly averages using summary statistics. Week 0 will be average of PPGA score from day -7 to day 1, week 1 will be average of score from day 2 to day 7, week 2 will be average of score from day 8 to day 14 and so on.

In addition, Spaghetti plot will be provided by subject and cohort and initial randomized treatment for PGA assessment and Physician's severity assessment of disease signs and symptoms

In the final analysis, shifts in PGA score from baseline to end of Epoch 4 by treatment group for each cohort will be shown in figures. , Summary tables of PGA after patients taking ACZ885 will be shown by visit, from Baseline to last visit in Epoch 4.

Episodes of Fever

Number and duration of fever episodes collected in patient's diaries will be summarized within each cohort, epoch and treatment group (as defined in [section 1.3](#)). Plots of fever episodes per patient over time (displaying frequency and duration) and treatment group will also be presented. Treatment difference for time to first resolution of fever will be analyzed using a Cox proportional hazard regression model. The Kaplan-Meier estimates of the proportion of patients with first resolution of fever along with the associated 95% confidence intervals using the Greenwood's formula will be provided.

Rescue medication

Corticosteroids levels will be summarized descriptively by analysis visit for each cohort and by treatment group (as defined in [section 1.3](#)). In addition, the number and percentage of patients who reduce their corticosteroids maintenance dose at Week 16 compared to baseline, patients who take corticosteroids rescue medication and patients who take only NSAIDs rescue medication during the study, patients who take steroid level >0.2 mg/kg/day will also be presented. Between-treatment differences for the proportion of patients who are able to reduce their corticosteroids at Week 16 will be analyzed using a Fisher's exact test for each cohort. The analysis will only include subjects who were receiving corticosteroids at baseline.

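### Section 5.5.9 requires study treatment to stop for any Table 5-1 treatment, but the table's corticosteroid-maintenance row says it need not stop; the two passages must be reconciled

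*Protocol*

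**What the plan says.** Protocol Section 5.5.8 states that use of the treatments in Table 5-1 "is NOT allowed after Screening". The first row is "Corticosteroid maintenance (prednisone equivalent > 0.2 mg/ kg/ day or greater than the maximum of 15 mg/ day for children over 60 kg"), and its action is "Investigational treatment does not need to be discontinued as a result of this protocol deviation (PD"). All the other rows call for study treatment to be discontinued. They include a separate row for "Intra-articular, peri-articular or intramuscular corticosteroid injections".

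Section 5.5.9 then gives a list headed "Investigational treatment must be discontinued under the following circumstances". One bullet is "Use of prohibited treatment as per" Table 5-1. It makes no exception for the corticosteroid row and does not mention the table's action column. The same section says that a patient who stops study treatment is not to be regarded as withdrawn from the study.

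The limit in that row is also the ceiling for steroid rescue. Section 5.5.6 permits "Increase of corticosteroid maintenance dose or intermittent steroid treatment up to the dose detailed in" Table 5-1.

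On the analysis side, SAP Section 1.10.5 plans to report such use descriptively: "patients who take steroid level >0.2 mg/kg/day will also be presented". Neither document gives an expected frequency.

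**The concern.** A site that works from 5.5.9 would stop study treatment in a patient whose maintenance steroid goes above the limit. A site that works from the first row of Table 5-1 would continue it. Both would be following the protocol as written.

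The situation can be foreseen, because the row's limit is the rescue ceiling and a raised maintenance dose is one of the two permitted forms of steroid rescue. What is at stake is consistency between sites and, for some patients, whether the outcome is observed and how it is classified. A stopped patient may have no further efficacy assessments and yet still be in the study, and the non-responder rule was not written for that state.

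**Working it through.** The documents state no figure to reproduce, so the check is a comparison of passages with one small piece of arithmetic.

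1. **Rows of Table 5-1.** There are 11. Ten carry an instruction to discontinue, in agreement with 5.5.9. One, corticosteroid maintenance above the limit, says discontinuation is not needed: 11 − 10 = 1 row in conflict.

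2. **What that row covers.** It covers corticosteroid maintenance only. Joint, peri-articular and intramuscular injections have their own row, which is marked for discontinuation, so the two passages agree there. Intermittent steroid rescue is capped by 5.5.6, but intermittent use above the cap has no action row of its own. The conflict is therefore confined to maintenance dosing.

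3. **The two instructions followed through.**
   - *Treatment stopped under 5.5.9.* Section 6.4 releases patients with a compulsory permanent stop from the efficacy assessments. Section 5.5.9 asks them back only for the assessments marked with an asterisk, and PGA has no asterisk in Table 6-1. The patient stays in the study.
   - *Treatment continued under Table 5-1.* The patient keeps the normal visit schedule, including PGA.

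4. **The classification rule.** Protocol Sections 9.4.1 and 9.4.3 and SAP Sections 1.10.1.1 and 1.10.1.3 impute non-response for dose escalation, for moving from placebo to canakinumab, and for discontinuing from the study. Stopping study treatment while remaining in the study is not on that list. The Week 16 secondary endpoints (Protocol 9.5.1) and the Epoch 3 responder analysis (SAP 1.10.2.1) use the same kind of wording.

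5. **Whose result could depend on the reading.** Not a patient whose index flare was unresolved at Day 15, who escaped, or who has already had a new flare; all of these are non-responders either way. What remains is a patient with a resolved index flare and no escape. For example, from Day 29 a patient with PGA of 2 or more but CRP below 30 mg/L meets neither the new-flare definition (6.4.5) nor the up-titration criterion (3.1.2.3), and could have the maintenance steroid raised. If treatment is then stopped, later PGA may be missing and no listed rule clearly applies.

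6. **Size per patient.** Section 4 plans 30 patients per arm in each cohort. One patient whose classification changes moves that arm's response rate by 1/30 = 0.033, or 3.3 percentage points. The number of such patients cannot be estimated from the documents, so no total follows.

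**The case against.** The best answer is that the 5.5.9 bullet points to Table 5-1, and a site that opens the table finds an action written for exactly this deviation. The cross-reference can be read as importing the action column, which would remove the conflict. The SAP sits more easily with that reading. It counts patients above 0.2 mg/kg/day descriptively, and the per-protocol criterion it spells out for failing to stop study drug (Table 1-1) concerns biologics only.

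This reading is plausible, and it makes the point an ambiguity rather than an unavoidable contradiction. It does not dispose of it. Section 5.5.9 never says that the action column governs, and the bullet stands under an unqualified requirement. The bullet that follows applies a test of significant safety risk to other deviations, while prohibited treatment is listed without one. The SAP does not instruct sites.

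It is also fair that Section 6.4 makes efficacy assessments unnecessary rather than forbidden, so a site may still collect them. And Section 3.1.2.2 directs rescue to patients who do not improve after the add-on injection, who are already non-responders. Both points stand, and they limit the effect on the primary result.

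A reader might go further and infer that exceeding the steroid limit is the commonest rescue problem, that it would fall mainly on placebo, or that every patient whose rescue exceeds the cap is handled in opposite ways. The documents support none of these. They give no frequency overall or by arm. The escape options shorten time on placebo. The row does not reach injected steroids, and it assigns no action to intermittent use.

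**Conclusion.** The point holds in a narrow form. For one of 11 rows, corticosteroid maintenance above the stated limit, Section 5.5.9 and Table 5-1 give opposite instructions when read literally, and nothing in either document says which prevails. Sites may therefore differ.

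The effect on the analysis is confined to patients who exceed the limit without having flared or escaped and who are then stopped. Each is worth up to 3.3 percentage points in an arm of 30. That rests on the planned arm size and on the non-responder rule being applied as worded, to leaving the study and not to stopping treatment. It would be wrong to conclude that the primary comparison is shown to be biased: the number of such patients is unknown, and most routes to rescue through escape already lead to non-response. This is an inconsistency of wording, not a flaw in the design, but it is worth correcting because the correction is so cheap. No view is taken on which instruction is clinically right.

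**What to change.** Reconcile the prohibited-treatment bullet in Section 5.5.9 with the action column of Table 5-1, so that both give the same instruction for the corticosteroid-maintenance row. The sponsor decides which passage changes.

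The cost is one phrase and a notice to sites. Section 11.1 requires changes to go through a written amendment, so the phrase can be carried in the next one. The design, sample size and planned analyses are unaffected.

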5.5.10 Withdrawal of consent

Patients may voluntarily withdraw consent to participate in the study for any reason at any time.

Withdrawal of consent occurs only when a patient does not want to participate in the study anymore and does not want any further visits or assessments and does not want any further study related contacts and does not allow analysis of already obtained biologic material.

If a patient withdraws consent, the investigator must make every effort (e.g. telephone, e-mail, letter) to determine the primary reason for this decision and record this information. Investigational treatment must be discontinued and no further assessments conducted. All biological material that has not been analyzed at the time of withdrawal must not be used. Further attempts to contact the patient are not allowed unless safety findings require communicating or follow-up.

5.5.11 Loss to follow-up

For patients whose status is unclear because they fail to appear for study visits without stating an intention to withdraw, the investigator should show "due diligence" by contacting the patient, family or family physician as agreed in the informed consent and by documenting in the source documents steps taken to contact the patient, e.g. dates of telephone calls, registered letters, etc. A patient should not be formally considered lost to follow-up until his/her scheduled end of study visit would have occurred.

5.5.12 Emergency breaking of assigned treatment code

Emergency treatment code breaks should only be undertaken when it is essential to treat the patient safely and efficaciously. Most often, investigational treatment discontinuation and knowledge of the possible treatment assignments are sufficient to treat a study patient who presents with an emergency condition. Emergency treatment code breaks are performed using the IRT. When the investigator contacts the system to break a treatment code for a patient, he/she must provide the requested patient identifying information and confirm the necessity to break the treatment code for the patient. The investigator will then receive details of the investigational drug treatment for the specified patient and a fax or email confirming this information. The system will automatically inform the Novartis monitor for the site and the Global Trial Lead (GTL) that the code has been broken.

It is the investigator's responsibility to ensure that there is a procedure in place to allow access to the IRT in case of emergency. The investigator will inform the patient how to contact his/her backup in cases of emergency when he/she is unavailable. The investigator will provide protocol number, investigational treatment name if available, patient number, and instructions for contacting the local Novartis Country Pharma Organization CPO (or any entity to which it has delegated responsibility for emergency code breaks) to the patient in case an emergency treatment code break is required at a time when the investigator and backup are unavailable.

5.5.13 Study completion and post-study treatment

A patient who completes the baseline visit, is randomized to study drug, continues to participate in all required study visits post randomization up to Day 113 and completes all required assessments is considered a study completer. Site personnel will complete the randomized treatment epoch completion form recording the date the patient last took study medication and whether the patient completed or discontinued from the study.

Enrollment in the screening portion of the study will be closely monitored when the 50th patient per cohort has been randomized. Patients still within the screening portion of the study will terminate their participation after the 60th, and last, patient per cohort has been randomized.

The investigator must provide follow-up medical care for all patients who are prematurely withdrawn from the study, or must refer them for appropriate ongoing care. This care does not require any special treatment but it is recommended not to initiate any live vaccination or biologic treatment until 3 months after the last dose of study treatment.

